1.1. Rationale and Objective: While there is support in the literature for beneficial effect of XO inhibitor therapy on GFR and BP in pediatric CKD, the degree of expected change in GFR based on disease etiology is uncertain. Therefore, we propose a randomized controlled trial of hyperuricemic pediatric CKD participants in a 2:1 allocation between Allopurinol and standard of care (SOC) therapy, and stratified by disease etiology (cohort A: non-glomerular, cohort B: glomerular). Randomization procedure will be blinded, but the allocation will be unblinded to investigator and participant because of the lack of placebo. Allopurinol will be titrated to reach a normal range of serum UA 3-5 mg/dL by 6 months. Local SOC practice for pediatric CKD includes control of blood pressure with anti-hypertensives, control of acidosis, control of proteinuria, and frequent laboratory monitoring to measure the rate of renal function decline. The primary outcome of Aim 1A is change in GFR between baseline and 6 months by treatment group. The secondary outcomes are change in serum UA, and change in BP over the same time. An exploratory sub-aim (Aim 1B) will identify and compare GFR change by cohort characteristics (disease etiology, proteinuria, and race) that may influence future trial designs.

1.2. Experimental Design (Table 1): We will conduct a 6-month randomized treatment (Allopurinol) vs. SOC clinical trial to measure change in GFR over time in pediatric hyperuricemic CKD participants. We will conduct this study after obtaining appropriate consent and assent. Our recruitment pool will include all patients receiving medical care from the CHoR Pediatric Nephrology Division, new and recurring outpatient encounters. The division currently sees approximately 3,500 outpatient encounters per year. The study visits will coincide with SOC visits with the possible exception of visit V1A (some but not all participants will normally be seen for SOC 1 month after the baseline visit). The following inclusion and exclusion criteria apply:

- Inclusion Criteria: CKD stage 1-5; Age 2-20 years old at time of enrollment; Hyperuricemic
- Exclusion Criteria: Contraindication to Allopurinol; Elevated baseline liver function tests; Receiving acute or chronic dialysis; Primary metabolic disorder; Sickle cell disease; Autosomal Dominant Polycystic Kidney Disease; Cystinosis; Bartter or Gitelman Disease; Pregnant or nursing.

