At baseline, demographic and anthropometric data, CKD disease etiology and duration since diagnosis, current medications, and presence of proteinuria or hypertension will be collected. At baseline and 6 months, casual clinic BP will be obtained (the average of three measurements) for hypertension assessment. Serum and non-invasively obtained urine will be collected at baseline, 3, and 6 months for basic or comprehensive metabolic panel, UA, cystatin C and creatinine-based GFR measurements. An additional serum and urine sample for purposes of dose titration and safety will be collected from the treatment group but not control at Visit V1A. The residual serum and urine samples will be bio-banked for the analyses of Aim 2. Adverse events will be collected and adherence will be measured at the V1A, V2, and V3 visits by pill count and through a validated visual analogue scale of adherence [26]. Participants will also receive a one-time monetary compensation at the conclusion of the study (V3).

Table 1. Study Timeline and Data Collection

Study Visit	Subject identification	Baseline Visit (V1)	Visit 1A (V1A)	Visit 2 (V2)	Endpoint Visit (V3)
Time	-1 to -3 months	0	+1 month	+3 months	+6 months
Encounter Purpose	1-3 month Allopurinol washout	Study enrollment, Randomization, baseline values	UA titration, Adherence & Safety check	UA titration, Adherence & Safety check	Study endpoint
Data Collection of Treatment group	C, G	A-E, G	D, F	C, E, F	A-F
Data Collection of Control group	C	A-E	No visit	C	A-E
Data Collection key	A: Demographic, anthropometric, medication history, clinic BP B: Vital signs including 3 casual clinic BP measurements C: Standard of care lab work: Serum – Basic metabolic panel, UA, cystatin C; Urine – Protein, creatinine, UA D: Serum Comprehensive metabolic panel; urine UA, creatinine. E: Reserve residual serum and urine samples for biomarker analysis F: Pill count, Adherence visual analogue scale, Evaluation of adverse events G: Urine pregnancy test if applicable to females of reproductive age				

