The investigational pharmacy (IP) will purchase the generic Allopurinol and Candesartan tablets, the cost of which is included in the IP’s administrative fees. This is a pilot clinical trial that uses a standard of care control group. It does not involve placebo encapsulation or blinding. The IP is responsible for packaging, labeling, and distributing the study drug Allopurinol as well as the concomitant therapy, Candesartan.

DOSING OF ALLOPURINOL: We will utilize a weight-based dosing strategy, starting at 5mg/kg/day divided twice daily. A maximum daily dose per day will be restricted at 400 mg per day. **Table 3** lists the starting dose by weight range.

Table 3. Allopurinol weight-based starting dose

Weight range	Dose
15-25 kg	50 mg TWICE DAILY
25.1 – 35 kg	75 mg TWICE DAILY
35.1 – 50 kg	100 mg TWICE DAILY
50.1 – 70 kg	150 mg TWICE DAILY

To target a uric acid level of 3-5 mg/dL used in this protocol, the Allopurinol dose will be escalated at Visit 1A and Visit 2 if the participant's uric acid level is >5 mg/dL. Similar to other Allopurinol dose escalation trials, the dose will be increased by 50mg/d for those participants with an estimated glomerular filtration rate (GFR) <60ml/min and 100mg/d in those with GFR ≥60ml/min.

DOSING OF CANDESARTAN: We will utilize an age and weight-based dosing strategy as recommended by the FDA dosing guidelines (**Table 4**). The participant's doctor is responsible for titrating Candesartan within the recommended dosing range to achieve the desired blood pressure control.

Table 4. Candesartan age and weight-based starting dose and dosing range

Age	Starting Dose	Titratable Dose Range
1 to <6 years	0.2 mg/kg once daily	0.05 – 0.4 mg/kg daily
6 to <17 years		
<50 kg	4-8 mg once daily	4-16 mg once daily
>50 kg	8-16 mg once daily	4-32 mg once daily
>17 years	16 mg once daily	8-32 mg total daily dose

DATA AND SAFETY MONITORING PLAN

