This randomized controlled trial aims to test the hypotheses that treatment of hyperuricemia with a xanthine oxidase inhibitor (Allopurinol) reduces the rate of decline of kidney function in chronic kidney disease, and markers of renal injury and inflammation. The Data and Safety Monitoring Plan (DSMP) is outlined below. During this study, all data collected will be kept confidential in an encrypted database using identification codes. Only approved research team members will have access to the database. The study staff will review all data collection forms on an ongoing basis for data completeness and accuracy as well as protocol compliance. Reviews of subject accrual, including compliance with protocol enrollment criteria and adherence data, will be performed by the PI and study staff on a monthly basis.

Data on adherence to the treatment protocol will be collected on an ongoing basis by research staff and reviewed quarterly by the PI. Adherence of participants will be evaluated by performing pill counts at study visits and by a validated visual analogue scale of adherence (patient self-report) at the end of study visit. An intention to treat protocol is applied to this study. However, if adherence falls below a rate of 75% which might inhibit the ability of the study to test its primary hypotheses, the study investigators and statistician will convene to discuss methods for improving adherence.

The PI will designate an Independent Monitor to perform an independent review of ongoing study progress and safety. The Independent Monitor will not be a part of the key research personnel, and will be qualified to review the patient safety data. Progress reports, including patient recruitment, retention/attrition of the study as a whole as well as retention of subjects undergoing washout or conversion therapy to study initiation, and adverse events (AE), will be provided to the Independent Monitor every 6 months. The reports will be generated only from aggregate for the entire study population. A closed safety report with masked group assignment will be generated for the Independent Monitor by an unmasked member of the study team (research coordinator).

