An Annual Report will also be compiled and will include a list and summary of AEs. In addition, the Annual Report will address (1) whether AE rates are consistent with pre-study assumptions; (2) reason for dropouts from the study; (3) whether all participants met entry criteria; (4) whether continuation of the study is justified on the basis that additional data are needed to accomplish the stated aims of the study; and (5) conditions

whereby the study might be terminated prematurely. The Annual Report will be sent to the Independent Monitor and will be forwarded to the IRB.

AE reports and annual summaries will not include identifiable material. Each report will refer only to the subjects' identification code. An AE is any untoward medical occurrence in a subject during participation in the clinical study or with use of the intervention agent being studied. An adverse finding can include a sign, symptom, abnormal assessment (laboratory test value, vital signs, skin reaction or physical exam finding), or any combination of these. A serious adverse event (SAE) is any adverse event that results in one or more of the following outcomes:

- Death
- A life-threatening event
- Inpatient hospitalization or prolongation of existing hospitalization
- A persistent or significant disability/incapacity
- A congenital anomaly or birth defect
- An important medical event based upon appropriate medical judgment

AEs will be labeled according to severity, which is based on their impact on the patient. An AE will be termed "mild" if it does not have a major impact on the patient, "moderate" if it causes the patient some minor inconvenience, and "severe" if it causes a substantial disruption to the patient's well-being. AEs will also be categorized according to the likelihood that they are related to the study intervention and labeled: definitely unrelated, definitely related, probably related, or possibly related to the study intervention. AEs will be reviewed with participants at each study visit.

Occasional 1-10% mild AEs are mild nausea, mild elevation in liver transaminase levels, and are not expected to impact a patient. These risks are considered minimal and will be addressed in the protocol and consent form.

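### As tabled, a second allopurinol escalation at month 3 comes with no scheduled liver result on the first escalated dose (minor, cheap to fix)

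*Combined protocol and SAP*

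**What the plan says.** The escalation rule is in Study Intervention Administration, Dosing of Allopurinol: "the Allopurinol dose will be escalated at Visit 1A and Visit 2 if the participant's uric acid level is >5 mg/dL". GFR sets only the size of the step (50 mg/day below 60 ml/min, otherwise 100 mg/day), and the daily dose is capped at 400 mg.

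Table 1 gives V1A and V2 the same purpose, "UA titration, Adherence & Safety check", and schedules item F (pill count, adherence scale, adverse-event evaluation) at both. The laboratory items differ. In the treatment arm, V1A has item D, the comprehensive panel. V2 has item C, which contains a basic panel, and not item D.

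Section 1.2 describes the extra draw at month 1 as follows: "serum and urine sample for purposes of dose titration and safety will be collected from the treatment group but not control at Visit V1A". For baseline, 3 and 6 months it lists "basic or comprehensive metabolic panel, UA, cystatin C and creatinine-based GFR measurements", without saying which panel applies at which visit.

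Liver safety appears in two other places. One exclusion criterion in section 1.2 is "Elevated baseline liver function tests". The Data and Safety Monitoring Plan names transaminase elevation at mild, moderate and severe levels. On the mild level it says: "Occasional 1-10% mild AEs are mild nausea, mild elevation in liver transaminase levels, and are not expected to impact a patient". It expects moderate events, as a group, in fewer than 1%.

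On adherence, the same plan says: "Adherence of participants will be evaluated by performing pill counts at study visits". Its one threshold applies to the study as a whole, "if adherence falls below a rate of 75% which might inhibit the ability of the study to test its primary hypotheses", and leads to a meeting about improving adherence.

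**The concern.** The protocol recognises the liver as a site of allopurinol toxicity: it excludes on baseline liver tests and lists transaminase elevation among the expected events. The dose can go up twice, at months 1 and 3. The month-1 liver result reflects the starting dose, so it says nothing about tolerance of the first increase. If month 3 brings only a basic panel, the second increase is made without that information, and the higher dose then runs to month 6 before the next scheduled liver test.

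A symptom such as rash or gastrointestinal distress can surface through the visit check or the telephone reports that participants are encouraged to make. A raised transaminase without symptoms cannot be found unless it is measured. What is at stake is the safety of a small subgroup of children. The sample size, the error rate and the primary comparison are not affected.

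**Working it through.** The plan states no figure for this interval, so there is none to reproduce. The check compares Table 1 with the dosing rule.

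**1. Scheduled liver results, treatment arm (Table 1)**

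| Visit | Month | Items | Item D? | Escalation possible? |
|---|---|---|---|---|
| V1 | 0 | A–E, G | yes | no (starting dose) |
| V1A | 1 | D, F | yes | first |
| V2 | 3 | C, E, F | no | second |
| V3 | 6 | A–F | yes | no |

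- Gap between liver results after V1A: 6 − 1 = 5 months.
- Age of the latest liver result at V2: 3 − 1 = 2 months, taken on the starting dose.
- Results on the first escalated dose available at V2: 0.

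With item D added at V2, the gaps are 3 − 1 = 2 and 6 − 3 = 3 months, so the longest is 3. One result on the first escalated dose is then available at V2.

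**2. Who can take a second step**

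Inputs are the starting doses in Table 3, the step by GFR and the 400 mg/day cap. The dose after k steps is the smaller of 400 and (start + k × step). Entries are mg/day at start / after V1A / after V2, if uric acid is above 5 mg/dL both times.

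| Weight | GFR <60 | GFR ≥60 |
|---|---|---|
| 15–25 kg | 100/150/200 | 100/200/300 |
| 25.1–35 kg | 150/200/250 | 150/250/350 |
| 35.1–50 kg | 200/250/300 | 200/300/400 |
| 50.1–70 kg | 300/350/400 | 300/400/400 |

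Seven of the eight paths leave room for a second step. The exception is 50.1–70 kg with GFR ≥60, where the cap is reached at V1A. The largest relative rise is 300/100 = 3 times the starting dose. The documents do not say how many participants will still be above 5 mg/dL at V2, so the number affected cannot be derived.

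**3. Expected yield**

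Table 2 puts 19 + 9 = 28 participants on allopurinol.

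- Moderate events of all types: below 28 × 0.01 = 0.28. This group also covers skin reaction and gastrointestinal distress, so moderate liver cases lie below 0.28.
- Mild elevation, if the 1–10% range is assumed to apply to it alone: 28 × 0.01 = 0.28 to 28 × 0.10 = 2.8. The plan does not expect these to matter to the patient, so a withholding rule needs a grade above mild.

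**4. Cost in tests**

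28 × 1 = 28 panels at most, if everyone on allopurinol reaches V2.

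**The case against.** The strongest reply is that Table 1 is loosely drafted and should not be read so literally. Item D at V1A lists urine uric acid but no serum uric acid, although the first escalation needs a serum value. Only the text of section 1.2, which gives that sample a titration and safety purpose, makes V1A work. The same section allows a comprehensive panel at 3 months, and Table 1 calls V2 a safety check. A comprehensive panel at V2 may therefore be intended. This stands as far as intent goes, and it means that nobody should infer that liver tests will in fact be absent for 5 months. What remains is that no text requires the panel at V2, and the one cell that specifies the visit omits it.

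Two further readings go beyond the documents. A reader might infer that both escalations lack a liver result on an escalated dose. At V1A nobody has yet been escalated, so none could exist; only the V2 decision is affected. A reader might also infer that clinicians must escalate despite missed pills or a suspected reaction. The rule states no such condition, but nothing bars judgement. Dosing is open-label, and uric acid, pill count and adverse events are all seen at V2. The investigator and staff also review adherence data monthly and adverse events on an ongoing basis. The unstated adherence condition is close to missing detail.

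The low expected yield also stands and limits the weight of the point.

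**Conclusion.** The point holds as a minor safety improvement to the schedule. It concerns participants who are escalated at V1A, remain above 5 mg/dL at V2 and are below the cap. For them, as tabled, the second escalation precedes any scheduled liver result on the first escalated dose.

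It rests on one assumption: that the comprehensive panel includes transaminases and the basic panel does not. The documents do not define either panel, but item D is the only laboratory item in Table 1 that could supply liver tests. If it did not, no liver test on treatment would be scheduled at all. Confidence is high that V2 lacks item D as written, and moderate that this would lead to missed testing in practice. No effect on the primary result is claimed, and the documents would not support one.

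**What to change.** 1. In Table 1, treatment row, change the V2 cell to C, D, E, F. The comprehensive panel replaces the basic one on the same draw; the other items of C stay.
2. Add to the Dosing of Allopurinol section: before any escalation at V2, review that visit's liver result and adverse-event evaluation. Do not escalate if there is a suspected drug reaction or a transaminase elevation above a grade set by the investigators. Mild elevation need not stop the drug.
3. Secondary suggestion only: check the pill count before escalating, and address poor adherence before raising the dose. The cut-off is for the investigators; the study-level 75% is one candidate.

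The cost is one table cell, one or two sentences and the upgraded panels, with no new visit. The V2 decision already waits for a uric acid result from that draw, so the liver result can be read with it. The downside is that V2 is the last titration visit. A dose kept there has no later scheduled escalation, so slightly fewer participants may reach 3–5 mg/dL by V3. Those participants stay in follow-up to V3 under the stated intention-to-treat policy.

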The rate of moderate AEs is expected to be <1%. The protocol includes measures to reduce the risk of moderate to severe AEs. Moderate AEs include skin reaction, gastrointestinal distress, moderate elevation in liver transaminases. Subjects will be encouraged to report these occurrences at any time during the intervention period by telephone within 24 hours of experiencing an event. Any adverse event rate over 5% in 12 months will be reported to the IRB.

Severe AEs include skin reaction as with development of Stevens-Johnson syndrome, or a significant elevation in liver transaminase levels that require hospitalization, and will be reported immediately to the IRB if this occurs. SAEs that are unanticipated, serious, and possibly related to the study intervention will be reported to the Independent Monitor and IRB in accordance with requirements. The Independent Monitor will be a clinician appointed by the PI who is not involved with the study design or analysis and is not a study investigator.

Unexpected fatal or life-threatening AEs related to the intervention will be reported to the IRB within 7 days. Other serious and unexpected AEs related to the intervention will be reported to the IRB within 15 days. Anticipated or unrelated SAEs will be handled in a less urgent manner but will be reported to the Independent Monitor and IRB. In the annual AE summary, the Independent Monitor Report will state that they have reviewed all AE reports.

The study staff, PI, and Independent Monitor will review the conglomerate adverse event rates every 6 months. Review of AE and SAE reports will also occur on an ongoing basis by the PI and study staff.

This study will be stopped prior to its completion if: (1) the intervention is associated with adverse effects that call into question the safety of the intervention; (2) difficulty in study recruitment or retention will significantly impact the ability to evaluate the study endpoints; (3) any new information becomes available during the trial that necessitates stopping the trial; or (4) other situations occur that might warrant stopping the trial.

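### The mild and moderate adverse-event grades overlap, and a silent moderate transaminase rise is mild by the plan's definition but moderate by its own example

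*Combined protocol and SAP*

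**What the plan says.** All the relevant text is in the Data and Safety Monitoring Plan of the combined protocol and SAP.

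- **Basis of grading.** "AEs will be labeled according to severity, which is based on their impact on the patient". No other basis is given.
- **The three grades.** An event is "termed 'mild' if it does not have a major impact on the patient, 'moderate' if it causes the patient some minor inconvenience". The third grade, severe, is kept for events that substantially disrupt how the patient is doing.
- **What counts as an adverse finding.** The definition expressly takes in an "abnormal assessment (laboratory test value, vital signs, skin reaction or physical exam finding".
- **Examples by grade.** Mild: mild nausea and a mild transaminase rise, neither expected to affect the patient. Moderate: "Moderate AEs include skin reaction, gastrointestinal distress, moderate elevation in liver transaminases". Severe: a skin reaction such as Stevens-Johnson syndrome, or "a significant elevation in liver transaminase levels that require hospitalization".
- **Expected rates.** 1-10% for mild events, below 1% for moderate events.
- **Use of the rates.** The Annual Report, which goes to the Independent Monitor and the IRB, must say whether event rates agree with what was assumed beforehand.

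The plan names no toxicity scale, sets no numeric laboratory limits, and does not define a mild, moderate or significant transaminase rise.

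**The concern.** A severity scale has to put each event in one grade. Here the mild grade is defined by the absence of a major impact, which is broad enough to take in everything the moderate grade describes. Two careful graders could file the same event differently, and both would be following the plan.

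There is a second problem for laboratory findings. The stated rule looks only at what the patient experiences, but the examples sort transaminase rises partly by how large they are. The two bases give different answers when a rise is moderate in size and has no effect on the patient.

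At stake is the safety comparison in the Annual Report. The expected rates are stated by grade, so the comparison can mean something only if the grades do. If staff follow the definition rather than the example, silent laboratory rises go into the lower grade and the moderate rate is understated.

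**Working it through.** The plan gives no figure to reproduce here; the check is mainly a comparison of texts.

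**Step 1. Do the definitions exclude one another?**

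| Event | Meets mild (no major impact)? | Meets moderate (minor inconvenience)? | Meets severe (substantial disruption)? |
|---|---|---|---|
| No effect on the patient | Yes | No | No |
| Minor inconvenience only | Yes | Yes | No |
| Substantial disruption | No | No | Yes |

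The second row meets two grades. Because a minor inconvenience is never a major impact, the moderate grade lies wholly inside the mild grade.

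**Step 2. Do the transaminase examples agree with the definitions?**

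| Example in the plan | Grade by example | Grade by definition | Agree? |
|---|---|---|---|
| Mild rise, no patient impact expected | Mild | Mild | Yes |
| Moderate rise, no effect on the patient | Moderate | Mild | No |
| Moderate rise, some inconvenience | Moderate | Mild and moderate | Ambiguous |
| Significant rise requiring hospitalization | Severe | Severe (hospitalization read as substantial disruption) | Yes |

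The conflict is at the mild/moderate boundary and nowhere else.

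**Step 3. Can the case arise?** Table 1 in section 1.2 schedules a comprehensive metabolic panel (item D) for the treatment group at V1, V1A and V3. I take that panel to be the source of the transaminase values. The post-baseline draws at V1A and V3 happen whether or not the child has symptoms, and the plan itself anticipates transaminase rises.

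**Step 4. How much can one grading decision move the reported rate?** Inputs: 28 allopurinol participants and 42 in all (Table 2), and the expected moderate rate of under 1%. The plan does not state a denominator, so both are shown.

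- One event among the treated: 1/28 = 3.6%.
- One event among all participants: 1/42 = 2.4%.

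Either exceeds 1%, so one event filed as moderate rather than mild puts the observed rate above the stated expectation.

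**Step 5. How much of that is sample size?** If the true moderate rate were exactly 1%, the chance of at least one such event would be 1 − 0.99^n:

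- n = 28: 1 − 0.99^28 = 24.5%.
- n = 42: 1 − 0.99^42 = 34.4%.

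A single moderate event is therefore weak evidence against the 1% assumption under any grading scale. Step 4 shows that the comparison is fragile; it is not a test.

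**The case against.** The strongest reply is that this is a drafting flaw with limited reach, and much of that reply stands.

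- **A reader might infer that silent rises are always graded mild, or become severe only on admission.** The documents do not support this. A grader who follows the named example would file a moderate rise as moderate. The severe list gives examples, and the definition remains substantial disruption. A rise with consequences for the patient is also no longer free of impact.
- **A reader might infer a conflict at the severe grade.** There is none. The severe liver example requires hospitalization, which fits substantial disruption.
- **A reader might infer that a liver signal could be hidden as expected mild events.** Two events in 28 is 7.1%, inside the 1-10% range. But the plan sends any adverse-event rate above 5% in 12 months to the IRB, with no restriction by grade, so on that denominator the rate is reportable. On all 42 participants, two events is 4.8% and three is 7.1%. The Annual Report also lists the events, the Independent Monitor must confirm review of every report, and the serious-event criteria are separate and include medically important events.
- **A reader might infer that a lower grade loses the 24-hour telephone report.** That report is made by the participant, who cannot report a rise that is not felt.
- **A reader might infer bias from open-label grading.** Table 1 schedules adverse-event evaluation (item F) only in the treatment group, and no between-arm safety comparison is specified. The argument adds little.
- **The move from 0% to 3.6% is mainly a small-sample effect**, as the working shows.

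What the reply does not remove is the contradiction. Definition and example give different grades for the same finding, and the safeguards above do not say which governs.

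**Conclusion.** The point holds at the mild/moderate boundary. The mild definition contains every event that meets the moderate one, and a moderate transaminase rise with no effect on the patient gets a different grade from the definition than from the example. This is a rule that contradicts itself, not merely a missing detail.

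Its practical effect is on the Annual Report's comparison with the grade-specific expectations. One event is worth 3.6 percentage points among 28 treated participants, or 2.4 among all 42, against an expected rate below 1%. The direction is downward for the moderate grade if staff apply the impact definition; if they follow the example, that rise is not shifted. The documents do not show which they would do, so a downward bias is a possible consequence and not a demonstrated one. With these numbers the comparison would be imprecise even under well-defined grades.

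The conclusion assumes that a minor inconvenience is not a major impact, that hospitalization is a substantial disruption, and that some rises found at V1A or V3 will have no effect on the child. Serious-event classification, the 5% rule and the efficacy analyses do not depend on the grade. The change should be made because the contradiction is plain and the remedy is cheap.

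**What to change.** Reconcile the severity paragraph of the Data and Safety Monitoring Plan with the example lists that follow it:

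1. Replace the three definitions with mutually exclusive grades from a named, published scale.
2. Grade laboratory events by value, using multiples of the laboratory's upper limit of normal fixed before enrolment. Because elevated baseline liver tests are an exclusion criterion (section 1.2), this reference suits the enrolled population.
3. Grade clinical events by their effect on function.
4. Rewrite the transaminase examples to match those limits, and restate the expected mild and moderate rates against the new grades, with the denominator given.

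The separate outcome-based definition of a serious event can stay as it is.

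The cost is rewording the monitoring plan and the adverse-event form. The laboratory values are already collected, and visits, sample size and analysis do not change. The downside is that some events may be graded higher, so the reported moderate rate may look slightly less favourable.
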